1.5.6. Infections

Infections (including sepsis, bacterial, viral, or fungal infections) were observed in subjects treated with ibrutinib therapy. Some of these reported infections have been associated with hospitalization and death. Consider prophylaxis according to standard of care in subjects who are at increased risk for opportunistic infections (reference [Section 6.1](#)). Although causality has not been established, cases of progressive multifocal leukoencephalopathy (PML) have occurred in patients treated with ibrutinib. Subjects should be monitored for symptoms (fever, chills, weakness, confusion) and appropriate therapy should be instituted as indicated.

1.5.6.1. Non-melanoma skin cancer

Non-melanoma skin cancers have occurred in patients treated with IMBRUVICA. Monitor patients for the appearance of non-melanoma skin cancer.

1.5.7. Rash

Rash has been commonly reported in subjects treated with either single agent ibrutinib or in combination with chemotherapy. Most rashes were mild to moderate in severity. Isolated cases of severe cutaneous adverse reactions (SCARs) including Stevens-Johnson syndrome (SJS) have been reported in subjects treated with ibrutinib. Subjects should be closely monitored for signs and symptoms suggestive of SCAR including SJS. Subjects receiving ibrutinib should be observed closely for rashes and treated symptomatically, including interruption of the suspected agent as appropriate. In addition, hypersensitivity-related events including erythema, urticaria, and angioedema have been reported.

1.5.8. Tumor Lysis Syndrome

There have been reports of tumor lysis syndrome (TLS) events in subjects treated with single-agent ibrutinib or in combination with chemotherapy. Subjects at risk of tumor lysis syndrome are those with comorbidities and/or risk factors such as high tumor burden prior to treatment,

increased uric acid (hyperuricemia), elevated lactate dehydrogenase (LDH), bulky disease at baseline, and pre-existing kidney abnormalities.

1.5.9. Interstitial Lung Disease (ILD)

Cases of interstitial lung disease (ILD) have been reported in patients treated with ibrutinib. Monitor patients for pulmonary symptoms indicative of ILD. Should symptoms develop follow the protocol dose modification guidelines (see [Section 5.3.1.4](#)).

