5.3.1.4. Dose Modification for Adverse Reactions

The dose of study drug should be modified according to the dose modification guidelines in Table 1 if any of the following toxicities occur:

- Grade 4 ANC (<500/ μ L) for more than 7 days or fibroneutropenia.
- Grade 3 thrombocytopenia (<50,000/ μ L) in the presence of clinically significant bleeding events.
- Grade 4 thrombocytopenia (<25,000/ μ L).
- Grade 3 or 4 nausea, vomiting, or diarrhea if persistent, despite optimal anti-emetic and/or anti-diarrheal therapy.
- Any other Grade 4 or unmanageable Grade 3 toxicity.

For Grade 3 or 4 atrial fibrillation or persistent atrial fibrillation of any grade, consider the risks and benefits of ibrutinib treatment. If clinically indicated, the use of anticoagulants or antiplatelet agents may be considered for the thromboprophylaxis of atrial fibrillation (Section 6.2.4).

Note: After a dose reduction, dose escalation of ibrutinib to a previous higher dose is NOT allowed.

Table 1. Ibrutinib Dose Modifications

Occurrence	Action to be Taken
First	Withhold study drug until recovery to Grade ≤ 1 or baseline; may restart at original dose level
Second	Withhold study drug until recovery to Grade ≤ 1 or baseline; may restart at 1 dose level lower (ie, 280 mg/day for 420 mg/day dose; 420 mg/day for 560 mg /day dose)
Third	Withhold study drug until recovery to Grade ≤ 1 or baseline; may restart at 1 dose level lower (ie, 140 mg/day for 420 mg/day dose; 280 mg/day for 560 mg /day dose)
Fourth	Discontinue study drug

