5.3.4.6. Pulmonary Toxicity

Severe pneumonitis or interstitial lung disease, including fatal cases, have occurred with nivolumab treatment. As such, patients must be monitored for signs and symptoms of pneumonitis. Across clinical trial experience in 691 patients with solid tumors, fatal immune mediated pneumonitis occurred in 0.7% (5/691) of patients receiving nivolumab. In one trial 2.2% (6/268) of patients receiving nivolumab developed immune-mediated pneumonitis, one with Grade 3 and with Grade 2 cases. In another trial, immune-mediated pneumonitis occurred in 6% (7/117) of patients receiving nivolumab including five Grade 3 and two Grade 2 cases.

Pulmonary toxicity should be managed according to the guidelines in Table 6.

Table 6 Dose Modification Guidelines for Pulmonary Toxicity

Description	Management	Follow-up
Grade I- radiographic changes only	
 - Consider withholding nivolumab. - Monitor every 2-3 days - consider pulmonary and infectious disease consults. 	
 - Reassess at least every 3 weeks - If improved, resume nivolumab (if it has been discontinued) when symptoms stabilized - If worsens, treat as Grade 2 or above
Grade 2: 
 - mild to moderate symptoms - radiographic changes 	
 - withhold nivolumab - monitor daily - consult Pulmonary and Infectious diseases - treatment with 1 mg/kg/day prednisone or equiv - consider bronchoscopy/lung biopsy 	If improved to baseline: 
 - taper steroids over at least 1 month before resuming nivolumab If not improving after 2 weeks or worsening: 
 - treat as Grade 3 or 4
Grade 3 or 4: 
 - severe symptoms - new/worsening hypoxia - life-threatening symptoms 	
 - Hospitalize patient - Permanently discontinue nivolumab - Monitor daily - Obtain Pulmonary and Infectious Disease consults - Treat with 1-2 mg/kg/day prednisone or equivalent - Consider bronchoscopy, lung biopsy 	If improved to baseline: 
 - taper steroids over at least 1 month If persists or worsens after 2 days 
 - add non-corticosteroid immunosuppressive medication

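### Symptomatic Grade 2 pneumonitis/ILD has no written ibrutinib hold, and at Grade 3 the hold depends on an undefined word

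*Combined protocol and SAP*

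**What the plan says.** Section 1.5.9 reports ILD in patients treated with ibrutinib, asks for monitoring of pulmonary symptoms, and adds: "Should symptoms develop follow the protocol dose modification guidelines", with a reference to Section 5.3.1.4.

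Section 5.3.1.4 says that the dose of study drug "should be modified according to the dose modification guidelines in Table 1 if any of the following toxicities occur". The list covers neutropenia, thrombocytopenia, persistent Grade 3 or 4 nausea, vomiting or diarrhea, and then "Any other Grade 4 or unmanageable Grade 3 toxicity". A separate note deals with atrial fibrillation. There is no lung item. Once a trigger is met, Table 1 holds ibrutinib until Grade 1 or less or baseline. After a first occurrence the patient "may restart at original dose level".

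Table 6 in Section 5.3.4.6 sets the lung rules by grade:
- **Grade 1** (radiographic changes only): consider withholding nivolumab.
- **Grade 2** (mild to moderate symptoms): "withhold nivolumab - monitor daily", give prednisone and, on improvement to baseline, "taper steroids over at least 1 month before resuming nivolumab".
- **Grade 3 or 4** (severe symptoms, new or worsening hypoxia, or life-threatening symptoms): hospitalize and "Permanently discontinue nivolumab".

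Table 6 does not mention ibrutinib.

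**The concern.** The protocol links both drugs to lung toxicity but sets lung-specific action grades for only one of them. A site that follows the written rules for a patient with symptomatic Grade 2 pneumonitis withholds nivolumab, starts steroids, and finds no instruction about ibrutinib. The default then favors continuing: Section 3.2.1 keeps ibrutinib going until progression, physician or patient choice, or unacceptable toxicity, and Section 9.2 item 8 lets a patient whose nivolumab has been held beyond 42 days remain on ibrutinib alone.

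This looks like an omission. Three ibrutinib risk paragraphs refer to the dose modification guidelines: atrial fibrillation (1.5.3), diarrhea (1.5.5) and ILD (1.5.9). Section 5.3.1.4 has specific text for the first two and none for ILD, although 1.5.9 is the only one of the three to give the section number.

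At stake are the safety of the individual patient and consistency: two investigators can handle the same event differently and both comply with the protocol.

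**Working it through.** **Step 1. What each rule requires for a lung event**

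| Event | Ibrutinib (5.3.1.4) | Nivolumab (Table 6) |
|---|---|---|
| Grade 1, radiographic only | no action stated | consider withholding |
| Grade 2, symptomatic | no action stated | withhold |
| Grade 3, judged manageable | no action stated | stop permanently |
| Grade 3, judged unmanageable | hold per Table 1 | stop permanently |
| Grade 4 | hold per Table 1 | stop permanently |

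The instruction in 1.5.9 is triggered by symptoms. In Table 6, symptoms start at Grade 2. The cross-reference therefore first applies at a grade for which 5.3.1.4 prescribes nothing.

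**Step 2. Does another section supply the missing hold?**
- 5.3.4: patients may suspend study treatment for related toxicity. This is permissive, sets no grade, and sits in the nivolumab section.
- 9.2 items 1, 3 and 5: stops based on judgement (unacceptable toxicity, an event preventing ibrutinib, investigator decision), with no grade.
- 6.4.1: ibrutinib is held at least 3 days before and after a minor procedure such as a needle biopsy. The procedure is the trigger, and Table 6 only asks that biopsy be considered.
- 5.2.1: a treatment-related Grade 3 or higher non-hematologic event in cycle 1 is a DLT. The readable text states no ibrutinib hold for that patient. The schema figure in 3.1.1 is not shown, so nothing is inferred from it.
- 12.4: at least monthly investigator meetings and monthly committee review of new drug-related serious events. These are oversight and not a dosing rule.

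None of these sets a Grade 2 ibrutinib hold.

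**Step 3. How often the Grade 2 gap would be met**

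Inputs: N = 30 (synopsis and 10.3) and the nivolumab trials in 5.3.4.6.
- Trial of 117: immune-mediated pneumonitis "occurred in 6% (7/117) of patients receiving nivolumab including five Grade 3 and two Grade 2 cases", so the Grade 2 rate is 2/117.
- Trial of 268: 6 cases, one of them Grade 3. The Grade 2 count is missing from the sentence and is taken as 6 - 1 = 5, so the rate is 5/268.

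Expected cases = N × p; chance of at least one = 1 - (1 - p)^N.
- 30 × 2/117 = 0.51; 1 - (1 - 2/117)^30 = 40%
- 30 × 5/268 = 0.56; 1 - (1 - 5/268)^30 = 43%

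**Step 4. How many patients a Grade 2 and Grade 3 hold would touch**
- 30 × 6/268 = 0.67
- 30 × 7/117 = 1.79

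Neither trial's breakdown includes a Grade 4 case.

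**The case against.** The strongest reply is that the cross-reference does reach a working rule. The last trigger in 5.3.1.4 is a catch-all for every organ toxicity not listed, so the absence of a lung item is not the absence of a rule, and asking for more is a preference for a lower threshold. At Grade 3 much of this stands. Table 6 describes severe symptoms or hypoxia and orders hospitalization, and an investigator could readily call that unmanageable. At Grade 2 it does not stand: the catch-all cannot apply, while the same protocol withholds the companion drug.

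A reader might infer from the table above that all Grade 3 lung events escape an ibrutinib hold, and might apply the same formula to the Grade 3 rates (1/268 and 5/117), which gives an 11-73% chance of at least one case. The documents do not support using that range as the size of the gap. They do not say what share of Grade 3 events would be judged manageable. The Grade 3 defect is that the word is undefined.

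A reader might also infer that continuing ibrutinib is known to worsen pneumonitis. The documents give no ibrutinib ILD rate, grade or fatality, and the fatal cases in 5.3.4.6 (5/691) are nivolumab cases.

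The rates are borrowed, too. Section 5.3.4.6 does not describe those patients as having renal cell cancer or receiving ibrutinib. That limits the figures to an indication of frequency and leaves the textual gap as it is.

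**Conclusion.** The point holds for Grade 2: no section gives a grade-based ibrutinib hold for symptomatic pneumonitis/ILD, although 1.5.9 sends such patients to the ibrutinib dosing rules. At Grade 3 the finding is narrower: a hold exists but depends on an undefined word, and after a first event Table 1 allows return to the original dose.

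About 0.5 Grade 2 cases are expected in 30 patients, with a 40-43% chance of at least one. This assumes that 30 patients are treated, that outcomes are independent, that the nivolumab rates carry over to the combination, and that the missing count in the trial of 268 is 5. The reading of the text needs none of these assumptions. No size of added harm is claimed, and investigators remain free to stop ibrutinib on judgement. This is a cheap improvement to patient safety.

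**What to change.** 1. **Table 6, Grade 2 row.** Add that ibrutinib is withheld until recovery to Grade 1 or less or baseline. State that this hold ends at recovery and not at the end of the steroid taper. Otherwise a taper of at least 1 month could carry the hold past 4 weeks, and 9.2 item 9 would then end nivolumab.
2. **Table 6, Grade 3-4 row.** Add that ibrutinib is withheld for every Grade 3-4 pneumonitis/ILD, as an instruction separate from the permanent nivolumab stop. State that the original-dose restart in Table 1 does not apply. The sponsor should specify either a lower-dose restart or a permanent stop; because nivolumab has already stopped at this grade, a permanent stop ends all study treatment.
3. **Section 5.3.1.4.** Cross-reference this rule and state whether a Grade 2 lung hold counts as a Table 1 occurrence.

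The edit is a few lines with no new procedures. Its costs are:
- Some lost ibrutinib exposure in about 0.67 to 1.79 of 30 patients at the nivolumab rates. Some of the Grade 3 holds may already occur today as unmanageable events.
- If Grade 2 holds count as occurrences, a second one lowers the dose, 5.3.1.4 forbids re-escalation, and a fourth ends ibrutinib.
- A hold that still passes 4 weeks ends nivolumab under 9.2 item 9, even though 3.2.1 (after two cycles) and 8.2 allow single-agent nivolumab. The amendment should say which governs.
- Ibrutinib may restart while steroids are being tapered, so these patients need infection monitoring; 1.5.6 lists infection as an ibrutinib risk.

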1.5.10. Hypertension

Hypertension has been commonly reported in subjects treated with ibrutinib. Monitor subjects for new onset of hypertension or hypertension that is not adequately controlled after starting ibrutinib. Adjust existing anti-hypertensive medications and/or initiate anti-hypertensive treatment as appropriate.

1.6. Study Rationale

The open-label, parallel assignment CheckMate-025 trial randomized 821 previously treated patients with advanced or metastatic clear-cell RCC to 3 mg/kg of IV nivolumab every 2 weeks or 10 mg of oral everolimus daily until progression or unacceptable toxicity. A trial combining nivolumab with the BTK/ETK inhibitor ibrutinib would be of great interest to the mRCC community.

2. STUDY OBJECTIVE

2.1. Primary Objective

To assess in a preliminary fashion the feasibility and efficacy of ibrutinib in combination with nivolumab in patients with previously-treated metastatic renal cell cancer (mRCC).

2.2. Secondary Objective(s)

To evaluate the safety of the combination of ibrutinib and nivolumab in patients with previously treated mRCC.

2.3. Exploratory Objective(s)

[figure not shown]
Archival tumor specimens will be collected for potential BTK.ETK and PD1 correlative studies.

3. STUDY DESIGN

3.1. Overview of Study Design

This is a prospective Phase Ib/II open-label, non-randomized, US multicenter study that is designed to test the efficacy of the addition of ibrutinib to nivolumab for the treatment of renal cell cancer.

3.1.1. Study Schema

*DLT assessment after 1 cycle (4 weeks)

*DLT = Grade III or higher SAE attributed to treatment

**Patients will have two de-escalation dose levels for (-1 and -2) for all patients based on interim toxicities.

3.2. Study Design Rationale

This is a prospective Phase Ib/II open-label, non-randomized, US multicenter study that is designed to test the efficacy of the addition of ibrutinib to nivolumab for the treatment of previously-treated renal cell cancer. The overall study plan will consist of a screening period, a study treatment phase, a follow up phase, if applicable, a safety follow-up and a survival follow-up. For safety, all patients will be followed for 30 days after the last dose of study treatment or until all treatment related clinical significant toxicities resolve to \leq grade 1. Survival status (date of death or date of last contact) will be recorded.

3.2.1. Study Population And Treatment

The study will enroll adult subjects with pathologically determined renal cell cancer. This study will be conducted at the University of California Davis Comprehensive Cancer Center and at another site that is yet to be determined. There will be a total of 2 US sites.

Ibrutinib in combination with nivolumab will be investigated. The assigned treatment (Ibrutinib in combination with nivolumab) will continue in subjects for a maximum of 1 year or until progression, unacceptable or intolerable toxicity, physician choice (if in best interest of patient), or patient withdrawal for any reason. In the event that the patient is unable (due to toxicity or tolerability issues) or unwilling to receive both agents concurrently after the first two cycles, then single agent nivolumab can be administered at the investigator's discretion to complete one year of therapy. Treatment with ibrutinib will continue until either disease progression OR physician/patient choice OR unacceptable or intolerable toxicities.

3.2.2. Dose Selection

The selected dose of ibrutinib ranges from 420-560 mg (2-4 x 140 mg capsules) once daily. Although ibrutinib is rapidly eliminated from the plasma after oral administration, once daily dosing with ibrutinib is adequate to sustain maximal pharmacodynamic activity for 24 hours postdose at dose levels \geq 2.5 mg/kg. A dose greater than 2.5 mg/kg was considered necessary to achieve consistent, full BTK occupancy, in previous PCYC studies. In Study PCYC-04753, the BTK occupancies for the 2.5 mg/kg/day to 12.5 mg/kg/day cohorts and for the 560 mg continuous dosing cohort, were all above 90% at either 4 or 24 hours after drug administration.

4. SUBJECT SELECTION

Patients will be recruited in the medical, urology, and radiation oncology clinics of the University of California Davis Medical Center and participating centers.

4.1. Inclusion Criteria

To be enrolled in the study, each potential subject must satisfy all of the following inclusion criteria.

Disease Related

Metastatic renal cell cancer patients (any histologic subtype) with measurable and/or evaluable disease who have completed at least one line of prior systemic therapy are potentially eligible for this trial. Any number of prior systemic therapies are allowed, including prior nivolumab.

Laboratory

1. Adequate hematologic function defined as:
 - Absolute neutrophil count $>750 \text{ cells/mm}^3 (0.75 \times 10^9/\text{L})$.
 - Platelet count $>50,000 \text{ cells/mm}^3 (50 \times 10^9/\text{L})$.
 - Hemoglobin $>8.0 \text{ g/dL}$.
2. Adequate hepatic and renal function defined as:
 - Serum aspartate transaminase (AST) or alanine transaminase (ALT) $\leq 3.0 \times$ upper limit of normal (ULN).
 - Estimated Creatinine Clearance $\geq 30 \text{ ml/min}$ (Cockcroft-Gault)
 - Bilirubin $\leq 1.5 \times$ ULN (unless bilirubin rise is due to Gilbert's syndrome or of non-hepatic origin)
3. PT/INR $<1.5 \times$ ULN and PTT (aPTT) $<1.5 \times$ ULN.

Demographic

4. Men and women ≥ 18 years of age.
5. Eastern Cooperative Oncology Group (ECOG) performance status of 0-2.

Ethical/Other

6. Female subjects who are of non-reproductive potential (ie, post-menopausal by history - no menses for ≥ 1 year; OR history of hysterectomy; OR history of bilateral tubal ligation; OR history of bilateral oophorectomy). Female subjects of childbearing potential must have a negative serum pregnancy test upon study entry.
7. Male and female subjects who agree to use both a highly effective methods of birth control (eg, implants, injectables, combined oral contraceptives, some intrauterine devices [IUDs], sexual abstinence, or sterilized partner) and a barrier method (eg, condoms, cervical ring, sponge, etc) during the period of therapy and for 30 days after the last dose of study drug

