4.2. Exclusion Criteria

To be enrolled in the study, potential subjects must meet NONE of the following exclusion criteria:

Concurrent Conditions

1. Cytotoxic chemotherapy \leq 21 days prior to first administration of study treatment and/or monoclonal antibody \leq 4 weeks prior to first administration of study treatment and/or other RCC-directed systemic therapy \leq 2 weeks prior to first administration of study treatment
2. Any known additional malignancy that is progressing or requires active treatment. Exceptions include basal cell carcinoma of the skin, squamous cell carcinoma of the skin, or in situ cervical cancer that has undergone potentially curative therapy.
3. Concurrent systemic immunosuppressant therapy (eg, cyclosporine A, tacrolimus, etc., or chronic administration [>14 days] of >10 mg/day of prednisone) within 28 days of the first dose of study drug.
4. Vaccinated with live, attenuated vaccines within 4 weeks of first dose of study drug.
5. Recent infection requiring systemic treatment that was completed \leq 14 days before the first dose of study drug.
6. Unresolved toxicities from prior anti-cancer therapy, defined as having not resolved to Common Terminology Criteria for Adverse Event (CTCAE, version 4), grade \leq 1, or to the levels dictated in the inclusion/exclusion criteria with the exception of alopecia.
7. Known bleeding disorders (eg, von Willebrand's disease) or hemophilia.
8. History of stroke or intracranial hemorrhage within 6 months prior to enrollment.
9. Known history of human immunodeficiency virus (HIV) or active with hepatitis C virus (HCV) or hepatitis B virus (HBV). *Subjects who are positive for hepatitis B core antibody or hepatitis B surface antigen must have a negative polymerase chain reaction (PCR) result before enrollment. Those who are PCR positive will be excluded.*
10. Any uncontrolled active systemic infection.
11. Major surgery within 4 weeks of first dose of study drug.
12. Any life-threatening illness, known autoimmune disease, medical condition, or organ system dysfunction that, in the investigator's opinion, could compromise the subject's safety or put the study outcomes at undue risk.

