5.3.3. Management of Nivolumab-Specific Adverse Events

Toxicities associated or possibly associated with nivolumab treatment should be managed according to standard medical practice. Additional tests, such as autoimmune serology or biopsies, may be used to determine a possible immunogenic etiology.

Although most immune-related adverse events observed with immunomodulatory agents have been mild and self-limiting, such events should be recognized early and treated promptly to avoid potential major complications. Discontinuation of nivolumab may not have an immediate therapeutic effect and in severe cases, immune-related toxicities may require acute management with topical corticosteroids, systemic corticosteroids, mycophenolate, or TNF- α inhibitors.

The primary approach to Grade 1-2 immune-related adverse events is supportive and symptomatic care with continued treatment with nivolumab; for higher grade immune-related adverse events, nivolumab should be held and oral/parental steroids administered. Recurrent Grade 2 immune-related adverse events may also mandate holding nivolumab or the use of steroids. Consideration for benefit/risk balance should be made by the investigator, with consideration of the totality of information as it pertains to the nature of the toxicity and the degree of clinical benefit a given patient may be experiencing prior to further administration of nivolumab. Nivolumab should be permanently discontinued in patients with life-threatening irAEs.

See Prescribing Information for full details.

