Grade 3 or 4 Grade 3 diarrhea: ≥ 7 stools per day over baseline, incontinence 
 - IV fluids ≥ 24 hs - Interferes with ADLs Colitis Grade 3: severe abdominal pain, medical intervention indicated, peritoneal signs present Colitis Grade 4: life threatening symptoms, perforation	Grade 3: withhold nivolumab until symptoms are Grade 1 Grade 3 persists or worsens, or Grade 4: permanently discontinue nivolumab Administer 1-2 mg/kg/day prednisone equivalents Consider lower-GI endoscopy	
If improved from Grade 3:
 
 - when at Grade 1, taper steroids over 1 month before resuming nivolumab 
If improved from persistent Grade 3 or Grade 4
 
 - continue steroids until Grade 1, then taper over at least 1 month 
If symptoms persist >3-5 days, or recur after improvement
 
 - add non-corticosteroid immunosuppressive medication

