5.3.4.3. Hepatotoxicity

Immune-mediated hepatitis has occurred with the administration of nivolumab.

Patients should be monitored for abnormal liver tests prior to and periodically during treatment. While on this study, patients presenting with right upper-quadrant abdominal pain and/or unexplained nausea or vomiting should have LFTs performed immediately and LFTs should be reviewed before administration of the next dose of study drug.

If LFTs increase, neoplastic, concurrent medications, viral hepatitis, and toxic etiologies should be considered and addressed, as appropriate. Imaging of the liver, gall bladder, and biliary tree should be performed to rule out neoplastic or other causes for the increased LFTs. Anti-nuclear antibody, perinuclear anti-neutrophil cytoplasmic antibody, anti-liver-kidney microsomal antibodies, and anti-smooth muscle antibody tests should be performed in an autoimmune etiology is considered.

Patients with LFT abnormalities should be managed according to the guidelines in Table 3.

Table 3 Dose Modification Guidelines for Hepatotoxicity

Symptoms	Management	Follow-up
Grade 1: AST or ALT >ULN to 3xULN and/or T Bili >ULN to 1.5xULN	Continue nivolumab Regularly monitor LFTs	Continue monitoring LFTs
Grade 2: AST or ALT >3 to \leq 5 x ULN and/or T Bili >1.5 to \leq 3 ULN	
 - Withhold nivolumab - Increase frequency of monitoring to every 3 days - 1 to 2 mg/kg/day prednisone equivalents 	If improved to Grade 1 or baseline, resume nivolumab. If steroids have been administered, taper steroids over at least 1 month before resuming nivolumab. Resume routine LFT monitoring
Grade 3 or 4: AST or ALT >5x ULN and/or T Bili >3x ULN	
 - Permanently discontinue nivolumab - Increase frequency of monitoring to every 1-2 days - Gastroenterology consult - Treat with 1-2 mg/kg/day prednisone equivalent 	If improved to <Grade 2, taper steroids over at least 1 month If labs persist >3-5 days, worsen or rebound: add non-corticosteroid immunosuppressive medication

IV = intravenous; LFT = liver function test; ULN = upper limit of normal.

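### Prior nivolumab is allowed and past toxicity need only have resolved, so a patient recovered from Grade 3-4 pneumonitis or hepatitis is kept out only by investigator judgement, although the protocol stops nivolumab for good if the same event occurs on study

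*Combined protocol and SAP*

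**What the plan says.** **Entry.** Section 4.1 sets no condition on how earlier nivolumab was tolerated: "Any number of prior systemic therapies are allowed, including prior nivolumab". In section 4.2, exclusion 6 is the only criterion on toxicity of earlier treatment. It bars "Unresolved toxicities from prior anti-cancer therapy, defined as having not resolved to Common Terminology Criteria for Adverse Event (CTCAE, version 4") Grade 1 or less, or to the levels set by the entry criteria, with alopecia excepted. Exclusion 12 bars "Any life-threatening illness, known autoimmune disease, medical condition, or organ system dysfunction that, in the investigator's opinion", could endanger the subject or the study outcomes. The synopsis version of that item leaves out autoimmune disease.

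**On study.** For Grade 3 or 4 hepatotoxicity, Table 3 in section 5.3.4.3 (not the response table with the same number in Appendix 4) says "Permanently discontinue nivolumab". Table 6 in section 5.3.4.6 gives the same instruction for Grade 3 or 4 pulmonary toxicity. Section 5.3.3 adds a general rule: "Nivolumab should be permanently discontinued in patients with life-threatening irAEs". For colitis and diarrhea, Table 2 reads "Grade 3 persists or worsens, or Grade 4: permanently discontinue nivolumab".

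**The concern.** The entry rule and the on-study rule treat recovery differently. Under exclusion 6, recovery is enough. Under Tables 3 and 6, recovery from a Grade 3-4 event does not reopen dosing. A patient whose severe event happened before enrollment can thus meet the objective criteria for a drug that the protocol would withdraw for good had the event happened a few months later.

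What is at stake is patient safety, not the primary analysis. Section 5.3.4.6 reports that immune-mediated pneumonitis on nivolumab has been fatal. Section 1.5.9 reports interstitial lung disease with ibrutinib, so re-exposure would come together with a second drug linked to lung injury.

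**Working it through.** The plan gives no figure for this point, so the check is mainly a comparison of rules.

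**Step 1. Take a patient who recovered from Grade 3-4 pneumonitis or hepatitis on earlier nivolumab through the criteria.**

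| Criterion | What it tests | Result |
|---|---|---|
| 4.1, prior therapy | Prior nivolumab allowed | Passes |
| 4.1, AST/ALT and bilirubin limits | Current laboratory values | Passes once recovered |
| Exclusion 1 | More than 4 weeks since last antibody | Passes after washout |
| Exclusion 3 | Prednisone above 10 mg/day for more than 14 days, within 28 days of first dose | Passes after taper |
| Exclusion 6 | Toxicity now Grade 1 or less, or at entry levels | Passes |
| Exclusion 21 | Currently active Child-Pugh B or C | Passes once recovered |
| Exclusion 12 | Investigator's opinion of risk | Depends on judgement |

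Every row except the last tests permission, time since treatment or present state. None tests the worst grade reached.

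**Step 2. Is the permanent stop deliberate?** In Table 3 the Grade 3-4 follow-up reads "If improved to <Grade 2, taper steroids over at least 1 month", with no step to resume. The Grade 2 row of the same table does provide for resuming nivolumab. Table 6 has the same pattern: Grade 2 has a taper before resuming, and Grade 3-4 has a taper only. The tables therefore distinguish events after which nivolumab may restart from events after which it may not.

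**Step 3. Do other provisions supply the missing rule?**
- Medical history (7.1.1.3) is to be complete and should reveal the event. The items named for prior treatments are dates, response and its duration, not toxicity or its grade.
- Central registration (Appendix 7, items D, F and G) checks eligibility and takes questions, but against the criteria as stated.
- Section 5.3.3 says "Consideration for benefit/risk balance should be made by the investigator, with consideration of the totality of information", but this guides management of events on study.
- Sections 5.3.2.1 and 5.3.3 refer to the nivolumab label, which is not among the documents. No entry criterion cites it.

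**Step 4. How many patients?** The expected number would need: 30 × share pretreated with nivolumab × probability of a past Grade 3-4 event among them × probability that exclusion 12 is not applied. The documents give only a partial input for the third factor. Section 5.3.4.6 reports Grade 3 pneumonitis in 1 of 268 patients in one trial and 5 of 117 in another. Setting the pretreated share to 1 and assuming exclusion 12 is never applied:
- First trial: 1/268 = 0.37%; 30 × 0.0037 = 0.11 patients.
- Second trial: 5/117 = 4.27%; 30 × 0.0427 = 1.28 patients.

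The two rates differ too much to pool (Fisher exact p = 0.011). The range 0.11 to 1.28 is an illustration, not a bound. The exact 95% upper limit from the second trial alone is about 2.9 in 30, and hepatitis is not counted because no rate is given. In the other direction, the real pretreated share is probably well below 1, since section 1.1.1 says nivolumab was not yet approved for metastatic RCC at the time of writing, and exclusion 12 would remove some of these patients.

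**Step 5. What the fatal cases show.** Fatal pneumonitis was reported in 5/691 = 0.7% of patients receiving nivolumab. That population is not patients re-treated after a severe event, and no recurrence rate is given. The figure shows that the event can kill. It does not measure the risk of re-treatment.

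**The case against.** The strongest reply is that exclusion 12 is binding and reaches this patient. An investigator who takes the full history, knows the stopping tables and can consult the coordinating site would have to judge a past Grade 3-4 pneumonitis or hepatitis to be no safety concern. Choosing judgement over a fixed rule is a legitimate design choice, few patients would be involved, and the endpoint, type I error and power are untouched.

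Much of this stands. A reader might infer that the criteria as written lead to re-dosing. They do not: exclusion 12 is one of those criteria, and re-dosing follows only if the investigator decides that it does not apply. A reader might also take 0.7% as the risk of death on re-treatment, or 1.28 patients as a worst case. Steps 4 and 5 show why neither reading is supported.

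What does not stand is that discretion closes the gap. Exclusion 12 names neither past immune-related events nor a grade, while exclusion 6 does address past toxicity and makes recovery sufficient. The protocol leaves no discretion over the same events on study. It also excludes on past events elsewhere, whether or not they have resolved: stroke or intracranial hemorrhage (exclusion 8) and myocardial infarction (exclusion 13), each within 6 months.

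**Conclusion.** The inconsistency is real and narrow. For Grade 3-4 immune-related pneumonitis and hepatitis on earlier nivolumab, the objective criteria admit a recovered patient, only investigator judgement stands in the way, and the same event on study ends nivolumab permanently. Section 5.3.3 extends the on-study rule to any life-threatening immune-related event.

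The conclusion rests on reading recovered to mean toxicity at Grade 1 or less or at entry levels, steroids within exclusion 3, and the antibody washout complete. Its size in patients is unknown. It is probably small, and the case for acting rests on the seriousness of the event rather than its frequency. Nothing here bears on the validity of the efficacy analysis. It is a cheap improvement.

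**What to change.** Add to section 4.2, and mirror in the synopsis: *Prior Grade 3 or higher immune-related pneumonitis or hepatitis, or any Grade 4 (life-threatening) immune-related adverse event, on nivolumab, even if resolved.* Add one line to the eligibility checklist required by Appendix 7, item C, recording the worst prior immune-related event and its grade.

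Keep the sentence to these events. A clause on Grade 3 colitis or diarrhea that persisted or worsened would require the time course to be reconstructed from old records. A clause on any event that led to permanent discontinuation would reach lower-grade histories, because section 5.3.4 discontinues nivolumab when adverse events hold it for more than 42 days. Extension to other PD-1/PD-L1 inhibitors is optional, since the conflict shown here concerns nivolumab.

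The cost is one sentence in two places and one checklist line, sent through section 12.9 (supplier review and approval, then IRB approval). Prior nivolumab stays allowed. The downside is that a few candidates may be lost.
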